The BART is a computerized measure of risk taking behavior developed by Lejuez et al. (2002). The BART models real-world risk behavior through the conceptual frame of balancing the potential for reward versus loss. In the task, the participant is presented with a balloon and offered the chance to earn money by pumping the balloon

up by clicking a button. Each click causes the balloon to incrementally inflate and money to be added to a counter up until some threshold, at which point the balloon is over inflated and explodes.

Thus, each pump confers greater risk, but also greater potential reward. If the participant chooses to cash-out prior to the balloon exploding then they collect the money earned for that trail, but if balloon explodes earnings for that trial are lost. Participants are not informed about the balloons breakpoints; the absence of this information allows for testing both participants' initial responses to the task and changes in responding as they gain experience with the task contingencies.

Reimbursement is based on the number of pumps accrued without the balloon exploding. Subjects will likely complete 30 trials and will be reimbursed for 5 cents per pump. This leads to an estimated reimbursement of \$10 per subject (expected range \$5 and \$20).

Behavioral Measures

As reviewed above, testosterone has been known to influence aggression, risk taking behavior, and empathy in human subjects. It is our intention to measure all three of these aspects to see if the behavioral effects of testosterone are manifesting at 3.5 hours as previous studies have established (See Appendix: Table of Past Studies). The behavioral tasks will consist of the Buss-Perry Aggression Questionnaire (Buss & Perry 1992; Bryant & Smith, 2001), which measures 4 domains of aggression that include: physical aggression, verbal aggression, anger, and hostility. Risk-taking behaviors will be measured using the Domain-Specific Risk-Attitude Scale (Weber, Blais, & Betz, 2002) that measures risk taking behavior over 5 domains that include: financial, health, ethical, recreational, and social risk-taking behaviors. The Body-Esteem Scale (Franzoi & Shields, 1984) is a 35 items scale used to measure how the participants feel about certain aspects of their bodies. The Self-Perceived Mating Success Scale (Landolt, Lalumière, & Quinsey, 1995) is a 12 item scale used to measure a participants self-perceived mating success. The SF-36 Health Survey (Ware & Sherbourne, 1992) is a 36 items survey and measures self-perceived physical and mental health. It is widely used in medical setting to assess patient's physical and mental health. Finally sexual attitudes and beliefs will be assessed using a scale developed by Gangestad, Simpson, cousins, Garver-Apgar, and Christensen (2004). Participants will be have to complete these behavioral tasks once in a single session. Once to establish a baseline and second to measure the effect of the drug/placebo (See Appendix: Flow Chart of Experimental Procedures). The order of the questions will be randomized each time. This is to ensure that the participants are not answering a question as they had previously answered it See Appendix: Behavioral Measures).

Feasibility

It is important to note, that the testosterone administration being proposed here is exactly the same to a previous study approved by this IRB (UNM Approval Code #902016-3). During the course of that previous study, none of the participants reported any ill effects from taking testosterone. With our previous experience, we feel that we can execute this protocol with minimum risk to the participants. The exact same researchers that worked on the previous study will also work on current study. These individuals will bring their experience and knowledge from the pilot study to this current study.

Compared to that previous study, this study is scaled down. Our Pilot study had 4 sessions consisting of 5 saliva samples per session. The current study, will only have 2 sessions with 2 saliva samples per session. The participants in the pilot study could receive the drug intervention (i.e. testosterone) twice during the course of the experiment. In the current study, they will only receive the drug intervention once. Therefore, the amount of risk to the participants is significantly reduced.

The pain component of this study is new, but our team has used this pain procedure in the past. In fact, we have published several papers using the ischemic pain task ([name] & Coulombe, 2011; [name] & Alcock, 2014; [name] [name], Trujillo, & Gangestad, 2014; [name], Rowell, & Lutz, 2014). Again, we feel confident that we can complete this protocol successfully with little risk to the participants.

I. *Target Population and Inclusion/Exclusion Criteria* College-aged females that are over the age of 18 and younger than 25 will be used for this study.

Exclusion Criteria:

All participants will be shown a list of exclusion criteria for this study on the Sona website. Before given the consent form the experimenter will go through this list to make sure the subjects do not meet any of the exclusion criteria. All women will be given a pregnancy test at each experimental session to ensure that the drug will not negatively impact an unborn child. If women are pregnant, they will be brought aside in the research lab and told they are pregnant and be given information on the Student Health and Counseling Center (SHAC) here on campus and excluded from the experiment. The following criteria will exclude a participant from the study:

> Anyone that has a tree nut allergy. Females that are pregnant or may feel that they may be pregnant or breast-feeding. Anyone taking supplements that may influence their testosterone level. Anyone taking any kind of steroid that may increase his or her testosterone level. Anyone that smokes tobacco or uses smokeless tobacco. Anyone that reports any condition associated with nerve damage. Anyone that is using hormonal contraceptive.

Each participant will complete a Testosterone Pre-Screen form (see Appendix). This form will ask each participant individually whether they are taking any drugs or have any conditions that might be exacerbated by testosterone. This form will be completed before they participate sign the consent form and each time they arrive in the lab for an experimental session.

- II. Participant Enrollment Twenty Female Participants will be enrolled in this study.
- III. *Recruitment and Screening Procedures* Participants will be recruited via the UNM Psychology SONA system.
- IV. Informed Consent Process

The participants have several opportunities to decide whether to continue or to terminate their involvement. Solicitations will operate through the SONA system, in which prospective participants are fully informed of the study protocol. All participants will attend a pre-lab session where only the consent form will be discussed. The experimenter will go through the consent form and make sure that the participant understands all that is required of them before they sign the consent form. Students will thus be allowed up to two weeks prior to a scheduled start date to decide whether they would like to participate in this study. I am also freely available to answer questions and concerns. Prior to their involvement in the study (upon arrival to the study location), participants are expected to provide written consent for the overall study (See Consent Form).

V. Data Collection Procedures

Described above in the Main Experiment Procedure. Two saliva samples will be collected during each of the 2 sessions that each subject attends:

- 1. Pre-Experiment saliva
- 2. Post Testosterone administration at 15 mins

Participants will also complete the pain task 4 hours following administration of T. Following the pain task, the behavioral measures will be administered at each experimental session to assess their state of aggression, risk-taking behavior, disgust, self-perceived health, self-perceived attraction, and sexual attitudes and beliefs. These surveys will be stored on an electronic survey site (Opinio) at UNM. We estimate that in all the experiment should take 5 hours to complete.

This same procedure will be repeated 3 days after the first experimental session.

VI. Study Timelines

The study will take approximately 12 months to complete starting from data collection and ending with the manuscript write up. It will take approximately 3 to 4 months to recruit and collect the data, and an additional month to 2 to 3 months to analyze the data and to process the biological samples, an additional month is needed to interpret the results, and finally and additional 3 to 4 months to prepare the manuscript write up. .

VII. Study Location(s)

The study will be conducted in the Pain Lab (Room B56) at Logan Hall on UNM Campus

VIII. Participant Compensation

Participants will be given 6 class credits (2 credits for 1st experimental session and 4 credits for the 2nd experimental session) for participation in this study and participants will be given \$5 for participating in each session of this study. Additionally, when participants preform the BART task they can earn between \$5 to \$20 per session. In total, participants can receive between \$10 and \$25 for each session they complete. In each session, participants will receive both the class credit and monetary compensation. The participants will be paid in cash. The class credit and the monetary compensation will be pro-rated based on the completion of each experimental session. If a participant fails to appear for an experimental session they will not be awarded credit or money for not showing up. If a participant decides to terminate the experiment during an experimental session they will be awarded credit and money for that session, but no further compensation will be provided if they do not complete the following experimental sessions. If participants terminate the session before they complete the BART, they will only be awarded the class credit for the session and the \$5.

If the participants are injured or become sick as a result of this study, the University of New Mexico Health Sciences Center (UNM HSC) will provide them with emergency treatment, at the patient's cost. The University makes no commitment to provide free medical care or money for injuries to participants in this study.

IX. Study Resources

The ideal research team consists of a tenured, Associate Professor and expert pain researcher with over 50 published scientific articles in the areas of psychology and pain perception, [name], and a Master's level graduate student with experience in running multiple types of social psychological and pain experiments, [name]. The researchers have protected research facilities and lab space for conducting the proposed experiments.

EXPECTED RISKS/BENEFITS

I. Potential Risks

The potential risks associated with the induction of 0.5mg Testosterone are not documented. Typical Testosterone Replacement therapies use a dosage that ranges from 10 mg to 200 mg (Bassil, Alkaade, & Morely, 2009). As such, the dosage used in the current study is miniscule in comparison. However, as with typical testosterone replacement therapies, the general risks include: increased aggression and increased libido, liver dysfunction, sleep apnea, edema may increase or worsen, gynecomastia, exacerbation of breast cancer, and finally skin irritation (Bassil, Alkaade, & Morely, 2009). However, it should be noted that these

side effects of testosterone only manifest after prolonged exposure to testosterone. Again, because we are only administrating two doses of 0.5mg Testosterone over a 4 day period, we feel that these potential risks will be minimal. The Table of Past Studies, which we have included in the Appendix , contains 6 studies where a similar experimental procedure was used. None of those studies reported any adverse problems to the participants and no participant dropped out of any of those studies due to complications of taking the T. Therefore, we believe that this experimental procedure is safe.

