The proposed study will consist of 2 experimental sessions where each participant will spend at most 5 hours per session. Prospective participants who meet our initial inclusionary criteria will come to the lab for a prelab session (See Appendix: Flow Chart of Experimental Procedures that Will Occur Over 4 Days for Each Participant). This session will be used to explain to the participants about the risks and benefits of participating in this study and to make sure they understand the time commitment. Once the prospective participants have read and stated they understand what is required of them, they will be allowed to sign the consent form and schedule their first lab visit. All lab visits will be determined based on the participant's menstrual cycle (See Appendix: Menstrual Cycle Scale). All female participants will visit the lab during their luteal phase of their menstrual cycle. The second lab visit will be 3 days after the first to ensure that the female participants are still in their luteal phase during the second lab visit. This will ensure that the changes in behavior and in pain are not the result of variations of within the menstrual cycle. At their first lab visit, participants will be pre-screened for pregnancy, tree nut allergies, and any use of drugs (e.g., Insulin, Blood-Thinners, Corticosteroids, Oxyphenbutazone, Triamcinolone) that may negatively interact with testosterone. After the first session, female participants will continue to be screened for pregnancy via a pregnancy test. Females who do test positive for pregnancy will be excused from the experiment and will be referred to the UNM Student Health and Counseling Center (SHAC) where they can seek further care. All participants will be inquired about any new medication use before the start of each session. Because exercise, sexual behaviors, and competitive activities may increase testosterone, all participants will be instructed to avoid these activities on the days that they participate in the experiment. Participants will also be asked to report the time they woke up in the morning to control for fluctuations in testosterone over the course of the day.

Participants will be randomly assigned to either a placebo group or a testosterone group before arrival. The experimenters will be blinded to this assignment. Randomization of the placebo and experimental drugs will be controlled by the research pharmacist.

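### Both pregnancy tests fall in one luteal phase, 3 days apart, so a conception in that cycle may test negative before dosing; a screening question would narrow the gap

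*Combined protocol and SAP*

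**What the plan says.** All references are to the combined protocol and SAP.

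- **Purpose of the test** (I. Target Population and Inclusion/Exclusion Criteria): "All women will be given a pregnancy test at each experimental session to ensure that the drug will not negatively impact an unborn child".
- **Visit timing** (II. Study Procedures, Main Procedure): "All female participants will visit the lab during their luteal phase of their menstrual cycle", and "The second lab visit will be 3 days after the first to ensure that the female participants are still in their luteal phase". The scheduling itself is referred to a Menstrual Cycle Scale in the appendix.
- **Consequence of a negative test** (Study Data, I. Data Management Procedures and Confidentiality): the test is thrown away and the woman proceeds.
- **Self-report safeguard** (exclusion list): "Females that are pregnant or may feel that they may be pregnant or breast-feeding".
- **Contraception** (exclusion list): "Anyone that is using hormonal contraceptive" is excluded. The text available requires no other method. The Main Procedure restricts sexual activity only on session days, and does so to keep testosterone stable.
- **Pre-Screen form**: completed before consent and "each time they arrive in the lab for an experimental session".
- **Dose and time course** (Participant Safety; I. Potential Risks): 0.5 mg, with testosterone described as back to normal 1.5 hours after administration.

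**The concern.** A pregnancy test cannot turn positive on the day of conception; some days must pass. The luteal phase is the stretch of the cycle just after ovulation, so a woman who conceived in the current cycle is tested when that pregnancy is hardest to see. The second test comes only 3 days later and is meant to be in the same phase. The text describes no test after the next expected period.

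A woman in this position could pass the test and receive a syringe that may hold testosterone, with nobody departing from the plan. A positive test at session 2 would come after her first syringe. At stake is a safeguard that the plan treats as protecting an unborn child. The scientific results are not at stake.

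**Working it through.** The plan gives no figure to reproduce. The check is one of timing.

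**Inputs from the documents.** Both visits are luteal. Visit 2 is visit 1 plus 3 days. A negative test leads to continuation.

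**Inputs the documents do not give.** Let *v* be the luteal day of visit 1, *d* the first day after ovulation on which a same-cycle conception can test positive, and *L* the length of the luteal phase.

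**Rule.** A test on day *x* misses if *x* < *d*. So visit 1 misses if *v* < *d*, and visit 2 misses if *v* + 3 < *d*. Because visit 2 must still be luteal, *v* ≤ *L* − 3.

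**Three cases follow.**
1. *v* ≥ *d*: neither test misses.
2. *d* − 3 ≤ *v* < *d*: session 1 misses and session 2 detects, after one syringe has been given.
3. *v* < *d* − 3: both tests miss.

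Anything missed at session 2 is also missed at session 1, since *v* + 3 < *d* implies *v* < *d*. The reverse does not hold. This is why session 1 is the weaker point, whatever the values.

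**Can the size be fixed?** Take, purely as an assumption, *L* = 14 and *d* anywhere from 8 to 14. The latest permitted visit 1 is day 14 − 3 = 11.
- Visit 1 on day 11, visit 2 on day 14: session 1 detects if *d* is 8 to 11 and misses if *d* is 12 to 14. Session 2 detects throughout.
- Visit 1 on day 1, visit 2 on day 4: both miss for every *d* from 8 to 14.

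The result therefore runs from no misses to misses at both sessions, depending on two quantities the text does not state. Any percentage would reflect an assumed visit schedule and not the plan, so none is given.

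**From a missed test to exposure.** Three further conditions must hold: the woman conceived in this cycle, self-report did not exclude her, and the syringe held active drug. The Feasibility section says the drug is received once, whereas Potential Risks speaks of two doses over the 4 days. The text therefore does not settle which sessions carry drug. A miss at a placebo session exposes nobody.

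**The case against.** The case for leaving the plan alone has several parts.

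- **Safeguards are layered.** The test is repeated, suspected pregnancy is an exclusion, and the Pre-Screen form is completed at each session. This stands as mitigation. However, feeling that one may be pregnant is a different question from possible conception in the current cycle, and before a missed period a woman may have no suspicion to report.
- **Unseen material may already cover it.** The Pre-Screen form, the behaviors survey, the Menstrual Cycle Scale and the consent text are not available here. This stands too: nothing can be said to be missing from them. The written exclusion criterion is in the text, though, and can be tightened regardless.
- **Dose and duration are small.** The Potential Risks section says "side effects of testosterone only manifest after prolonged exposure to testosterone" and reports no adverse problems in six similar studies. This bears on severity. Those statements do not address pregnancy, and the plan itself makes pregnancy a reason to exclude.
- **The sentence states a purpose, not test accuracy.** That is a fair reading, and changing the verb alone would be editorial. The timing gap is there under either reading.

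A reader might go further and infer that the tests are worthless, that most same-cycle conceptions would be missed, or that fetal harm is likely. The documents support none of these. A pregnancy from an earlier cycle should be detectable at both sessions, the miss rate is indeterminate and could be nil with late-luteal visits, and nothing in the text shows harm to a fetus from this exposure.

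**Conclusion.** The point holds in limited form and is minor. Testing twice within one luteal phase cannot by itself rule out a conception from that cycle, and the stated self-report exclusion covers the gap only in part. The conclusion rests on the plan's own visit timing and on one outside premise, that a test needs some days after conception before it can be positive. It does not rest on any particular detection day or luteal length.

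No number of affected women among the 20 can be estimated. The consequence is further limited by the 0.5 mg dose and its short-lived rise, and arises only where active drug is given.

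**What to change.** Keep the luteal timing and the hormonal-contraceptive exclusion.

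1. Reword the pregnancy exclusion so that it covers possible conception since the last period, for example unprotected intercourse in the current cycle.
2. Ask this on the Pre-Screen form at each session, if it is not already there.
3. Defer women who answer yes to a later cycle.

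The cost is one reworded criterion and at most one item on a form already in use. Some women will be deferred, so recruiting 20 may take slightly longer. The answer remains self-report and will not catch, for instance, contraceptive failure, so the risk is reduced and not removed.

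Softening the claim that the test ensures protection is an optional wording change and would not do the job alone.

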
Experimental studies in females has found that women with higher basal levels of testosterone show higher levels of what are generally considered protypical male behaviors, and repeated experiments have replicated similar effects. For example, a study looking at dominance in females found that females with high levels of testosterone attributed more dominant characteristics to themselves than women with lower levels of testosterone (Grant & France, 2001). Female twins with a male twin brother show higher mean levels of aggression than same-sex, female twins, and this has been attributed to testosterone exposure in the womb (Cohen-Bendahan, Buitelaar, van Goozen, Orlebeke, & Cohen-Kettenis, 2005). Under controlled laboratory conditions, females that are given low doses of testosterone show reductions in empathetic behaviors (Hermans, Putman, & van Honk, 2006; van Honk, Schutter, Bos, Kruijt, Lentjes, & Baron-Cohen, 2013; Montoya, Terburg, Bos, Will, Buskens, Raub, van Honk, 2013). A logical extension of the above described work as it relates to sex differences in pain perception is to use a controlled laboratory experiment to examine how ephemeral and thus safe, short-lasting testosterone induction interacts with naturally circulating basal levels of testosterone to influence external pain sensitivity as part of a broad spectrum of changes in social behaviors associated with fluctuating testosterone levels.

OBJECTIVES/AIMS/HYPOTHESES

Our hypotheses are that: a) Females with high levels of circulating salivary (basal) Testosterone levels will experience reduced pain tolerance (hypoanalgesia) in a ischemic pressure pain task (primary outcome); b); Testosterone will alter the participants basal levels of estradiol and progesterone (secondary outcome) c): Further, exploratory outcomes will test whether testosterone will increase risk-taking behaviors, aggression, perception of health, attractiveness, disgust response, and sexual attitudes and beliefs.

STUDY DESIGN AND PROCEDURES

I. Study Design

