The drug will be attained from the UNM Research Pharmacy that will prepare both the placebo and the drug for the purposes of this study (See Appendix: Letter from Research Pharmacist). The researchers will be blinded to this study. On the day of the experiment, the medical doctor on staff will write an individual prescription for the subjects participating in the study that day. The researchers conducting this study will then present the prescriptions to the UNM Research Laboratory and pick up the drug for the purposes of this study. Each subject will have an individual syringe prepared for them in which they will self-administer with directions from the researchers of this study. When the drug/placebo is in the lab it will be secured in a locked cabinet in our lab facilities; however, only testosterone/placebos being used for that days session will be stored at our lab . Only authorized lab personnel and/or medical personnel will have access to the drug at any time and a log will be kept indicating the inventory of the drug and when the drug has been removed from the cabinet and used. In the case that an unauthorized removal of the drug occurs (i.e. theft) or if there is indication that the log has been fabricated, the IRB will be notified immediately.

Participant Safety. Previous research has established that the current protocol will increase circulating levels of testosterone in the body by a factor of 10 within 15 mins of administration with baseline levels of testosterone returning to normal in 1.5 hrs after administration. As noted, however, behavioral effects of .5 mg of Testosterone reach their maximum levels 3-4 hours after administration (Tuten, van Honk, Koppeschaar, Bernaards, Thijssen, & Verbauten, 2000). Several studies using this same procedure for administration for Testosterone have found it to be a safe and effective means of administration for women with no ill effects or complications being reported by the authors as described in the form in the Appendix called "Table of Past Studies" (van Honk, Schutter, Bos, Kruijt, Lentjes, & Baron-Cohen, 2011; Montoya, Terburg, Bos, Will, Busken,

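### The risk section ties aggression and libido effects to prolonged exposure, while the protocol tests for acute behavioural effects of 0.5 mg and, in the visible text, schedules no symptom question

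*Combined protocol and SAP*

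**What the plan says.** **Potential Risks** (Expected Risks/Benefits, I). For testosterone replacement therapies, "the general risks include: increased aggression and increased libido", followed by six physical effects. The text then says that these "side effects of testosterone only manifest after prolonged exposure to testosterone" and, given the small amount used, that the risks should be minimal. The same section says that the risks of 0.5 mg are not documented.

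**Testosterone Administration, Participant Safety.** Hormone levels are described with "baseline levels of testosterone returning to normal in 1.5 hrs after administration", but "behavioral effects of .5 mg of Testosterone reach their maximum levels 3-4 hours after administration". This part also holds the list of side effects that subjects are to be told of, described there as belonging to stronger, repeated hormone treatment.

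**Objectives/Aims/Hypotheses.** "exploratory outcomes will test whether testosterone will increase risk-taking behaviors, aggression", among others.

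**Behavioral Measures.** Aggression, risk-taking and empathy are measured "to see if the behavioral effects of testosterone are manifesting at 3.5 hours as previous studies have established".

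**Session length.** The Main Procedure states that "each participant will spend at most 5 hours per session". Data Collection Procedures agrees: "We estimate that in all the experiment should take 5 hours to complete". The post-dose pain task comes 4 hours after administration and the behavioural measures follow it.

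**Unanticipated Problems/Adverse Events.** The study is terminated if a participant claims significant psychological or physical distress that goes on for more than 1 hour after taking part. Unanticipated problems go to the IRB within 24 hours.

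**The concern.** The same effect is treated in two ways. In the risk section, aggression belongs to a list that short exposure cannot produce. In the objectives and methods, it is an outcome to be looked for a few hours after one administration. A reader weighing the risk, including an ethics board or a participant, gets the first account, while the scientific case rests on the second.

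The safety provisions in the visible text then depend on the participant. The termination and 24-hour reporting rules need to hear about distress that, by definition, is still present an hour after the session. If nobody asks, a report of no adverse effects cannot be told apart from a failure to ask.

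**Working it through.** The documents give no figure to reproduce here. The check is a comparison of sections plus simple arithmetic.

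**1. Can the two accounts both hold?**

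| Question | Potential Risks | Other sections |
|---|---|---|
| Is aggression an effect of testosterone? | Yes, first in the list | Yes, as a directional exploratory outcome |
| When can it occur? | Only after prolonged exposure | Behavioural maximum 3-4 hours after 0.5 mg; battery aimed at 3.5 hours |
| Use made of this | Risks called minimal | Timing of the test battery |

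The number of administrations is itself stated differently: once under Feasibility and in the Participant Safety text, two doses over 4 days under Potential Risks. This does not resolve the conflict, because Potential Risks itself treats two doses as short of prolonged exposure.

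**2. Do the two risk lists agree?** Potential Risks names 8 items: aggression, libido, liver dysfunction, sleep apnea, edema, gynecomastia, exacerbation of breast cancer and skin irritation.
- With a counterpart in the list for subjects: liver function, fluid retention, breast enlargement, skin irritation = 4 of 8.
- Without one: aggression, libido, sleep apnea, breast cancer = 8 - 4 = 4 of 8.
- Risk-taking, an outcome under test, is in neither list.
- Male-only items in the list for subjects: abnormal erection, inflamed testes, prostatic growth = 3, in a study that enrols only women.

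**3. How long after the stated maximum do women leave?** Let R be the time from dose to release. The pain task is at 4 hours, so R is above 4. The session lasts at most 5 hours and some procedures come before the dose, so R is no more than 5.
- Maximum at 3 hours: R - 3 is at most 5 - 3 = 2 hours.
- Maximum at 4 hours: R - 4 is at most 5 - 4 = 1 hour.

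The gap is therefore at most 1-2 hours. Baseline saliva, screening and pre-dose procedures shorten it. No section says when the behavioural effect ends. The 1.5-hour hormone figure does not supply that, because the plan's own behavioural maximum comes later.

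**4. Where is a participant asked about symptoms?**

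| Point | What the visible text schedules |
|---|---|
| Before release, each session | Aggression, risk-taking and self-perceived health, as outcomes; no stated safety review |
| Arrival at session 2, 3 days later | New medication, pre-screen form on drugs and conditions, pregnancy test, consent reminder |
| After session 2 | Debriefing form with contact details; the participant must make contact |

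The distress rule needs more than 1 hour to pass after participation, so it will normally be met, if at all, after the woman has left. None of the three rows describes a question that would pick this up.

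**The case against.** The case on the other side has real substance.

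- **Contact and measurement exist.** A reader might infer that women are released unchecked and not seen again. The documents do not support that. Aggression, risk-taking and health status (SF-36) are measured before release, everyone is due back after 3 days, and a debriefing form gives contact details. What stands is narrower: these measures are outcomes with no stated review, and none of these contacts is described as a symptom inquiry.
- **Forms are not shown.** A reader might also infer that adverse events are solicited in none of the 40 planned sessions (20 women x 2), or that the consent form hides the behavioural effects. Neither can be shown. The pre-screen form, debriefing form, flow chart and consent form were not available, and the consent form has its own risk section, since the protocol says that it will carry a dosing-error warning. The omission is established only for the protocol body.
- **The list for subjects is not empty on this point.** It names anxiety, excitation, confusion and sexual dysfunction, and its origin in stronger therapy may explain the male-only items. Those entries are still not the effects under test.
- **The outcomes are exploratory.** To say that the study expects aggression to rise is too strong, and a questionnaire shift is not in itself an adverse event. The direction is nonetheless stated and the timing is treated as established.
- **The maximum falls on site.** This is so on the plan's figures. It does not follow that the effect outlasts the session, or that it does not: no end time is given.
- **Earlier experience was reassuring.** The pilot and the cited studies reported no problems. It would be speculation to say that nobody asked in those studies; the documents do not describe how events were collected. The dose comparison and this experience remain as support for a low risk.

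**Conclusion.** The concern holds in a limited form. The protocol contradicts itself on whether aggression and libido effects can follow short exposure, and one part of its argument for minimal risk uses the side of the contradiction that its own objectives do not share. The list for subjects lacks 4 of the 8 risks named in the risk section and includes 3 that cannot apply to women. Release comes at most 1-2 hours after the stated behavioural maximum. In the visible text, no symptom question is scheduled at release, on the day-3 return or after session 2, while the termination rule relies on a participant's own claim.

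This rests on three assumptions: that the risk-section sentence refers back to the whole list, as its wording indicates; that the session limit covers everything from arrival to release; and that the forms not shown contain no symptom question or fuller risk list. If they do, the monitoring and disclosure parts shrink, but the contradiction remains. Nothing here shows that the administration is unsafe or which time course is correct. The primary pain analysis is unaffected. The change should be made because it is cheap and the existing safety rules depend on it.

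**What to change.** 1. Reconcile Potential Risks with Objectives, Participant Safety and Behavioral Measures on when behavioural effects can occur. The sponsor decides what the reconciled text says.
2. Align the list for subjects and the consent form with that text and with an all-female sample.
3. Add one short open symptom question (what, when it began, how long, whether still present) to the existing electronic survey at the end of each session, ask it again on arrival at session 2, and send it in one message after session 2. Answers go to the investigator under the existing adverse-event and IRB rules.

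Cost: wording changes in the protocol and possibly the consent form, one survey item, and one message per participant. Per woman there are 2 end-of-session prompts + 1 on arrival + 1 message = 4; for 20 women, 4 x 20 = 80. Asking will bring in a few more minor reports. No dose, release time or stopping rule is proposed.
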